## 4. Statistical Considerations

### 4.1. General Considerations

All key data collected on case report forms will be presented in the data listings and will be listed and sorted by treatment arm, participant number and (where applicable) visit. All descriptive summaries will be presented by treatment group and (where applicable) nominal visit/time point.

All safety and descriptive summaries will be presented by treatment group. All disposition and concomitant medication descriptive summaries will be presented by treatment sequence and nominal visit/time point (where applicable).

Unless otherwise stated, the following methods will be applied:

- **Continuous variables:** Descriptive statistics will include the number of non-missing values (n), arithmetic mean, standard deviation (SD), median, minimum and maximum values.

The minimum and maximum values will be displayed to the same decimal precision as the source data, the arithmetic mean, SD and median values will be displayed to one more decimal than the source data for the specific variable.

95% Confidence Intervals (CIs), mean differences (among treatments and from baseline) and least-square (LS-Means) values will be displayed to one more decimal than the source data for a specific variable. P-values will be displayed to 3 decimal places.

The appropriate precision for derived variables will be determined based on the precision of the data on which the derivations are based, and statistics will be presented in accordance with the afore-mentioned rules.

- **Categorical variables:** Descriptive statistics will include counts and percentages per category. The denominator in all percentage calculations will be the number of participants in the relevant analysis population with non-missing data, unless specifically stated otherwise. Percentages will be displayed to one decimal place. Proportions will be displayed to 3 decimal places.

95% Confidence Intervals (CIs), difference in proportions, odds ratios and other categorical parameters will be displayed to one decimal place for percentages. Proportions will be displayed to 3 decimal places. P-values will be displayed to 3 decimal places.

No inferential statistics will be produced for any safety endpoints.

- **Repeat/unscheduled assessments:** Only values collected at scheduled study visits/time points will be presented in summary tables. Unscheduled visit data may be included in summaries of baseline, minimum/maximum post-baseline, and incidence of subjects with potentially

clinically significant post-baseline results. Unscheduled visits will also be presented in the applicable data listings.

- Assessment windows: Data will be summarized using the recorded nominal visit values in the CRF; no visit date windowing will be conducted. All assessments will be included in the data listings.
- Date and time display conventions: The following display conventions will be applied in all outputs where dates and/or times are displayed:

Date only: YYYY-MM-DD

Date and time: YYYY-MM-DD HH:MM

If only partial information is available, unknown components of the date or time will be presented as 'NK' (not known), i.e., '2016-NK-NK'. Times will be reported in military time.

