## METHODOLOGY

**General Experimental Design:** This will be a randomized, double-blind, placebo-controlled study of ATL5 (CBD) (600 mg/day, [300 mg twice daily]) as adjunctive therapy to buprenorphine or methadone for patients with OUD, who are receiving inpatient behavioral therapy, including cognitive behavioral therapy.

**Endpoints:** The primary endpoint will be safety and tolerability of CBD in these patients, and it will be assessed via measurement of adverse events. Pharmacokinetic analyses will evaluate potential drug-drug interactions of CBD with buprenorphine metabolism. The secondary outcome measure will be cue-induced craving for opioids, assessed using the Desires for Drug Questionnaire (DDQ) in the context of an opioid cue-induction paradigm in the laboratory session before CBD dosing on Day 0 (baseline without CBD) to scores on Days 7 and 28 (after adjunctive treatment with CBD) (*see Criteria for Evaluation below*).

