From May 2022 through May 2023, 28 participants were randomized 2:1 CBD 600 mg:placebo; however, 6 of these participants did not receive any study drug.

Towards the end of enrollment of the first dose cohort, it became clear that financial constraints would preclude study of a higher dose cohort. In June 2023, randomization was reversed to 2:1 placebo:CBD to increase power by balancing the low CBD and placebo groups as much as was

possible in the remaining time. From June 2023 through January 2024, 7 participants were randomized 2:1 placebo:CBD 600 mg. This SAP is based on the study plan that includes these modifications. It is expected that there will be 21 patients in the 600-mg CBD arm ( $28*0.67+7*0.33$ ), and 14 patients in the placebo arm ( $28*0.33+7*0.67$ ).

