### 3.4. Objectives and Endpoints

Objectives	Endpoints
Primary: To evaluate the safety and tolerability of CBD in the study population.	Primary: Number of treatment-emergent adverse events over the 28-day treatment period by study arm. Secondary: Changes in liver enzymes, pulse oximetry, sedation, and cardiovascular measures (heart rate, blood pressure, and cardiac rhythm and conduction on EKG).
Secondary: To determine the extent to which CBD (600 mg/day) reduces cue-induced craving for opioids relative to placebo.	Primary: Cue-induced craving for opioids, assessed using the Desires for Drug Questionnaire (DDQ)  in the context of an opioid cue-induction paradigm, assessed in the laboratory session before CBD dosing on Day 0 (baseline without CBD) and on Days 7 and 28 (after adjunctive treatment with CBD) Secondary: Spontaneous opioid craving, assessed using the Penn Alcohol-Craving Scale, as modified to assess opioid craving;  affect, assessed using the Positive and Negative Affect Schedule (PANAS),  Anxiety, assessed by state subscale of the Spielberger State-Trait Anxiety Inventory,  Percentage of patients with increase in their buprenorphine dose, Treatment retention, as indicated by number of days of continued participation
Exploratory: A. To evaluate effects of CBD on metabolism of other endocannabinoids, i.e., N-arachidonylethanolamide (anandamide) and 2-arachidonoyl-glycerol (2-AG) levels. B. To assess pharmacokinetics of CBD in patients receiving buprenorphine for treatment of OUD.	Plasma levels of anandamide and 2-AG. CBD pharmacokinetics—time to reach steady state and accumulation parameters (C max , AUC 0-24 ). In addition, the buprenorphine/norbuprenorphine ratio will be determined to evaluate potential drug-drug interactions of CBD with buprenorphine metabolism (dealkylation). Although this ratio does not, by itself, an increase in the ratio, concurrent with the emergence of hypoxia and/or sedation would be an AE.

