## **5. Analysis Populations (Analysis Sets)**

The randomized population will include all subjects randomized regardless of whether they had any study drug.

The safety population will include all subjects who received at least one treatment of study drug and will be used for the summaries of all baseline, demographic, and safety data.

The full analysis set (FAS) population is a subset of safety population and consists of those that have at least one post-baseline efficacy measurement. This population will be used for the summaries of all efficacy data.

The pharmacokinetic (PK) population is a subset of the safety population and consists of those who have at least one PK assessment.

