### **10.1. Adverse Events**

AEs related to study procedures will be collected from the signing of the ICF through the end of the study. An adverse event (AE) will be recorded if it is a new event that was not present at Screening or is the worsening of an event present at Screening.

All AEs included will be coded using MedDRA. All AE summaries will be restricted to TEAEs only. Summary tables will include the number of participants (%) experiencing an event and the number of events. Participants will be counted only once for each SOC and PT level (categorical descriptive analysis). When TEAEs are reported by relatedness and/or severity, each TEAE will be counted once per subject at the worst/highest level of the assessment (e.g., highest relationship to investigational device or greatest severity).

The MedDRA version used for reporting will be described in the relevant table and listing footnotes.

The TEAE summaries will include:

- Overall summaries of TEAEs.
- TEAE summaries by SOC and PT.

A comprehensive listing of all adverse events will be provided in a by-subject data listing.

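### The primary safety endpoint is a between-arm comparison of adverse events, but the SAP provides no measure of its precision

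*SAP*

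**What the plan says.** The two documents agree that safety comes first. The Protocol (Methodology, Endpoints) says: "The primary endpoint will be safety and tolerability of CBD in these patients, and it will be assessed via measurement of adverse events". SAP 3.4 states the primary objective as "To evaluate the safety and tolerability of CBD in the study population" and its primary endpoint as "Number of treatment-emergent adverse events over the 28-day treatment period by study arm". That endpoint is a count of events, and it is compared between arms.

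SAP 4.1 gives general formatting conventions, including "95% Confidence Intervals (CIs), difference in proportions, odds ratios and other categorical parameters will be displayed to one decimal place for percentages". The part of 4.1 on continuous and categorical variables closes with "No inferential statistics will be produced for any safety endpoints". SAP 10.1 sets the content of the adverse-event tables: "Summary tables will include the number of participants (%) experiencing an event and the number of events". Neither 10.1 nor the sections on laboratory values and vital signs (10.2, 10.3) asks for a difference, a ratio or an interval.

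On numbers, SAP 5 says "The safety population will include all subjects who received at least one treatment of study drug". SAP 3.1 reports 28 participants randomized 2:1 in favour of CBD, of whom "6 of these participants did not receive any study drug", and then 7 randomized 2:1 in favour of placebo.

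**The concern.** The objective ranked first receives the least analysis. Craving, the secondary objective, gets a repeated-measures model with 95% intervals (SAP 11). The exploratory endocannabinoid levels also get a model (SAP 12). The primary adverse-event comparison gets counts and percentages. No tolerability criterion, margin or precision target is set anywhere, and the sample size rests on craving alone (SAP 3.5).

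In a safety population this small, the observed percentages say little without their uncertainty. Two arms can look alike while the data remain compatible with a large excess of events on CBD. An event type that is never seen may still be fairly common. A report that follows the SAP exactly would state neither limit. The raw count has a further problem: the arms are unequal in size and participants can leave early, so numbers of events cannot be compared without a denominator of exposure.

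**Working it through.** **The plan's own figures.** SAP 3.1 expects 28 × 0.67 + 7 × 0.33 = 21.07 on CBD and 28 × 0.33 + 7 × 0.67 = 13.93 on placebo, which reproduces 21 and 14. The only sizing figure is power of 0.80 for craving at d = 1.0 (SAP 3.5). With noncentrality √(14 × 21 / 35) = 2.90 and 33 degrees of freedom, the t test gives 0.803, so it reproduces. There is no corresponding figure for safety.

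**Size of the safety population.** At most 28 − 6 + 7 = 29. The arms of the 6 undosed participants are not stated. If they divide 2:1 and all 7 later participants were dosed:

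- CBD: 22 × 2/3 + 7 × 1/3 = 17.0
- Placebo: 22 × 1/3 + 7 × 2/3 = 12.0

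With 21/14 randomized, the extremes are 15/14 (all 6 undosed on CBD) and 21/8 (all 6 on placebo).

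**Event types never seen on CBD.** The two-sided exact 95% upper limit for 0 of n is 1 − 0.025^(1/n), and the chance of missing a true 5% event altogether is 0.95^n.

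| n on CBD | Upper limit for 0/n | Chance of missing a 5% event |
|---|---|---|
| 15 | 21.8% | 46% |
| 17 | 19.5% | 42% |
| 21 | 16.1% | 34% |

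**Participants with at least one TEAE.** The documents give no expected rates, so these counts are illustrations. The Newcombe interval for p1 − p2 has upper limit d + √[(u1 − p1)² + (p2 − l2)²], where l and u are Wilson limits. For 10/17 vs 7/12, the Wilson limits are 0.360 to 0.784 and 0.320 to 0.807, and d = 0.005. The upper limit is 0.005 + √[(0.784 − 0.588)² + (0.583 − 0.320)²] = 0.333.

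| CBD vs placebo | Difference (points) | 95% CI (points) |
|---|---|---|
| 10/17 vs 7/12 | +0.5 | −31 to +33 |
| 9/17 vs 6/12 | +2.9 | −30 to +35 |
| 8/15 vs 7/14 | +3.3 | −30 to +35 |
| 11/21 vs 4/8 | +2.4 | −32 to +37 |

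**Number of TEAEs, the endpoint as worded.** Suppose both arms have r events per person, with r assumed. The 95% interval for the rate ratio runs from 1/F to F, with F = exp{1.96 × √[v × (1/n1 + 1/n2)]}. Here v = 1/r for Poisson counts and v = 1/r + 1 for negative binomial counts with an assumed dispersion of 1. At 17 vs 12, 1/17 + 1/12 = 0.1422.

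| r | F, Poisson | F, dispersion 1 |
|---|---|---|
| 1 | 2.09 | 2.84 |
| 3 | 1.53 | 2.35 |

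The split matters little here. For r = 1 and Poisson counts, F is exp(1.96 × √(1/15 + 1/14)) = 2.07 at 15/14 and exp(1.96 × √(1/21 + 1/8)) = 2.26 at 21/8.

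**The case against.** Descriptive safety reporting is normal in a small phase 2 trial sized on another outcome, and this SAP specifies it openly in advance. The sentence in 4.1 does not name confidence intervals, and the same section has a display format for them. Counts, percentages and denominators will be tabulated, so a reader can compute an interval for any proportion. By-subject listings, laboratory and vital-sign summaries and the abnormality criteria of Appendix B add detail. The Protocol's primary objective also covers the buprenorphine interaction, for which SAP 12 does compare the groups by ANCOVA.

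Much of this stands. No hypothesis test is needed, no data are lost, and the no-inference rule touches only the safety part of the Protocol's primary objective. It does not remove the point. A format for intervals does not require one, and no safety section asks for one. If descriptive intervals are meant to be allowed, the SAP should say so for its primary endpoint. A reader can rebuild an interval for a proportion from the tables. An interval for the event rate also needs the spread of counts between people and the time at risk, which the summary tables do not give.

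A reader might infer that the plan means to treat similar counts, or zero events, as proof of tolerability. The documents do not say this: they expect CBD to be well tolerated but set no rule for concluding it. A reader might also take 17 vs 12 as the actual split, or take the SAP to prohibit intervals in terms. The first is an assumption. The second depends on the ordinary reading of the word inferential.

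**Conclusion.** The point holds as a gap in reporting for the primary endpoint. On the ordinary reading of SAP 4.1 together with 10.1, the primary between-arm comparison carries no measure of precision, and nothing in the plan states what the data could rule out.

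With at most 29 participants the uncertainty left unstated is large. The exact upper limit for an unseen event on CBD is 16% to 22%. Near-equal participant percentages around 50% to 60% allow a CBD excess of about 33 to 37 points. At equal event rates, the TEAE rate ratio is uncertain by a factor of about 1.5 to 2.8 either way.

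The first two ranges cover every split from 15/14 to 21/8. The third is for 17 vs 12 and assumes 1 to 3 events per person, with variation from Poisson to dispersion 1. All event frequencies are illustrations. The safety data themselves remain valid, so this should be corrected but does not undermine the trial.

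**What to change.** Replace the closing sentence in SAP 4.1 with wording such as:

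> No hypothesis tests will be done on safety endpoints. For the primary endpoint, the TEAE rate per person-time over the 28-day treatment period will be given per arm, with the between-arm rate ratio and its 95% CI, allowing for overdispersion. The proportion of participants with at least one TEAE, and with each PCSA category, will be given per arm with a Clopper-Pearson 95% CI, and the between-arm difference with a Newcombe 95% CI. Any statement on tolerability will quote the upper confidence limit of the between-arm comparison or, for categories with zero events, the exact upper limit in the CBD arm.

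Repeat the requirement in 10.1 and name the rate model there, for example negative binomial with log time at risk as offset. Intervals for every system organ class and preferred term are not needed; they would add many wide rows and little information.

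The cost is a change of SAP wording and a few table columns, with no new data, visits or participants. The real downside is that wide intervals will make the safety conclusion look less favourable than bare percentages would.

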## 4.2. Handling of Missing Data

For the classification of Treatment emergent adverse event (TEAE) and concomitant medication, the following will be applied in the described order:

- a. If all dates/times (start and stop) are missing, the event/medication will automatically be classified as a TEAE/concomitant medication.
- b. For AEs with a missing start date/time, if the event end date/time is prior to first instillation, the event will not be classified as a TEAE.
- c. If only the AE start year/ medication end year is present and is the same or is after the first instillation year unit, the event/medication will be classified as a TEAE/concomitant medication.
- d. If the AE start month and year/medication end month and year are present and are the same or after the first instillation month and year units, the event/medication will be classified as a TEAE/concomitant medication.

## 4.3. Conversion of categorical values

In some instances, continuous variables are expressed as a range (i.e., < 10). In such cases, values may be converted to the range boundary (upper or lower limit as applicable). As an example, a value of <10 may be converted to 10. Such substitutions will be clearly documented in the footnotes of relevant outputs.

## 4.4. Coding of Events and Medications

Medical history and AE verbatim terms will be coded using the Medical Dictionary for Regulatory Activities (MedDRA) version 26.1. Terms will be coded to the full MedDRA hierarchy, but the system organ class (SOC) and preferred terms (PT) will be of primary interest for the analyses.

Prior and concomitant medications will be coded using the World Health Organization Drug Dictionary. Medications will be mapped to the full WhoDrug Anatomical Therapeutic Chemical (ATC) class hierarchy, but PTs will be of primary interest in this analysis.

## **5. Analysis Populations (Analysis Sets)**

The randomized population will include all subjects randomized regardless of whether they had any study drug.

The safety population will include all subjects who received at least one treatment of study drug and will be used for the summaries of all baseline, demographic, and safety data.

The full analysis set (FAS) population is a subset of safety population and consists of those that have at least one post-baseline efficacy measurement. This population will be used for the summaries of all efficacy data.

The pharmacokinetic (PK) population is a subset of the safety population and consists of those who have at least one PK assessment.

## **6. Disposition**

Participant disposition will be based on the randomized population and include the number in each of the other study populations, as well as the number of subjects that completed each of the study visits, and, for those who did not, the reason for early withdrawal. A listing corresponding to the disposition table and a listing for screen failures will be provided.

## **7. Protocol Deviations**

Prior to database lock, all protocol deviations will be reviewed by medical monitor and assigned a status of minor or major. A listing of all major protocol deviations will be provided.

## **8. Demographic and Baseline Characteristics**

Subject demographics and baseline characteristics will be summarized and listed. Medical history, the psychological evaluation, and the MINI will also be summarized and listed. In both cases, this will be based on the randomized population.

## **9. Study Drug Exposure**

Study drug exposure will be summarized and provided in a listing, based on the randomized population.

## **10. Safety**

Safety endpoints will be analyzed using the Safety population.

### **10.1. Adverse Events**

AEs related to study procedures will be collected from the signing of the ICF through the end of the study. An adverse event (AE) will be recorded if it is a new event that was not present at Screening or is the worsening of an event present at Screening.

All AEs included will be coded using MedDRA. All AE summaries will be restricted to TEAEs only. Summary tables will include the number of participants (%) experiencing an event and the number of events. Participants will be counted only once for each SOC and PT level (categorical descriptive analysis). When TEAEs are reported by relatedness and/or severity, each TEAE will be counted once per subject at the worst/highest level of the assessment (e.g., highest relationship to investigational device or greatest severity).

The MedDRA version used for reporting will be described in the relevant table and listing footnotes.

The TEAE summaries will include:

- Overall summaries of TEAEs.
- TEAE summaries by SOC and PT.

A comprehensive listing of all adverse events will be provided in a by-subject data listing.

## **10.2. Safety Laboratory Assessments**

Only key lab parameters as outlined in Appendix A will be provided in a table. These results will be summarized and provided in a listing.

Pregnancy test data (urine and serum based) findings will be presented in by-subject data listings for any non-negative result.

## **10.3. Vital Signs**

The following vital signs measurements will be taken at the time points specified in the Schedule of Events (refer to the Protocol): Height (cm), Weight (kg), Heart Rate (beats/min), Systolic blood pressure (SBP) (mmHg), Diastolic blood pressure (DBP) (mmHg), Respiratory rate (breaths/min), Temperature (°C). All vital signs data will be summarized and included in the listings.

## **10.4. Concomitant Medications**

Concomitant medications will be summarized by indication and drug name, as well as provided in a listing.

# **11. Efficacy**

All efficacy analyses will be based on the Full Analysis Set Population and Efficacy endpoints will be summarized descriptively. Absolute change and percent change will be reported for all efficacy endpoints. All efficacy data will be provided in listings.

### **Primary Efficacy Target**

**Desire for Drug Questionnaire (DDQ):** The DDQ is a 14-item scale used to assess cue-induced craving, administered here in the context of a laboratory-based opioid cue-induction paradigm. All responses are scored on a Likert scale from "strongly disagree" (1) to "strongly agree" (7). A table will be provided with summaries per visit (Baseline, 7, and 28 days), as well as absolute and percent changes from baseline, for the DDQ Total Score of Opiate Use (subscale including 7 items, primary endpoint) and the DDQ Total Score (all 14 DDQ items, secondary endpoint), both of which will be used to assess cue-induced craving, our primary efficacy target. For each outcome, we will run a mixed model for repeated measures (MMRM), with change from baseline as the outcome; fixed effects for treatment, time, and a treatment by time interaction; and an appropriate random effects/covariance structure to account for within-subject correlations. In addition, figures, based on the MMRMs will be provided: 1) by treatment, and 2) for the difference between treatments, both with 95% model estimate confidence intervals. The primary efficacy outcome is the MMRM model estimate for change from baseline in cue induced craving at 28 days between the two treatment groups.

